8.3 Mediation analyses

If a significant association is observed between any diet group and hip fracture in the main analysis (with regular meat-eaters as the reference group), we will further explore the potential mediating

effect of variables that have previously been associated with – or could plausibly be associated with – diet groups and hip fracture risk. Potential mediators include (all measured at recruitment):

- Potential anthropometric mediators: BMI, BMD (at the heel and femoral neck depending on availability of data and number of participants with each measure), bone mineral content, lean muscle mass, hand grip strength, and fat mass;
- Circulating vitamin D and IGF-1 levels;
- Total energy intake and dietary intake of protein, calcium, vitamin B12, and omega-3' fatty acids.

For each potential mediator, we will explore whether it is more appropriate to use measures at recruitment (extrapolated to represent measures during the study period), or to calculate changes in the mediator variable of interest from recruitment to the latest measurement during follow-up, depending on the availability of mediator data in UK biobank participants.

To determine if each of the potential mediators listed vary by diet group, multiple linear regression will be used, adjusting for relevant confounders. We will not explore mediation if there is no significant difference in risk of hip fracture across diet groups, or if the mediator is not significantly different between each diet group and regular meat-eaters.

We will test for mediation using the inverse odds ratio weighting (IORW) method, which estimates the natural direct and indirect effects of potential mediators, and is described in detail elsewhere (5-7).

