2.0 Study design

The dataset will use participant data from the pre-existing UK Biobank database. This is a prospective cohort of over 500,000 adults across England, Scotland, and Wales, aged 40 – 69 years at recruitment in 2006-2010. Participants were recruited via National Health Service (NHS) patient registers, and attended one of 22 assessment centres across the UK, where participants were asked to complete a touchscreen questionnaire, verbal interview, physical measures, and a biosample collection (more information available at [UK Biobank - UK Biobank](#)).

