5.0 Outcomes

The primary outcome will be first incidence of hip fracture (ICD-9 code 820 and ICD-10 codes S72.0-S72.2) identified using hospital inpatient data for England, Scotland, and Wales. This includes Hospital Episode Statistics for England until 30th September 2021, Scottish Morbidity Records for Scotland until 31st July 2021, and the Patient Episode Database for Wales until 28th Feb 2018. The timeframe will be person-years until hip fracture incidence, or until end of study period or death in non-cases, calculated as age at time of event or censoring minus age at study entry. Sources and dates of availability for each region’s hospital inpatient data (and therefore censoring dates) are presented in Table 2.

Table 2: Hospital inpatient data in England, Scotland, and Wales.

Country	Data source	Period of time for which data is available
England	Hospital Episode Statistics (HES)	1997 – 30 th Sept 2021
Scotland	Scottish Morbidity Record (SMR)	1981 – 31 st July 2021
Wales	Patient Episode Database for Wales (PEDW)	1998 – 28 th Feb 2018

Adapted from: [External Info : Data providers and dates \(ox.ac.uk\)](#)

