11.1.2 Anthropometrics

Body mass index (BMI), height, and weight

Body weight and standing height were measured at the assessment centre visit at recruitment. BMI was calculated as a participant’s body weight (kg) divided by the square of their height (m).

Other body composition measures

Bioimpedance was measured at the assessment centre visit at recruitment using the Tanita Bc418ma bioimpedance device, from which body fat percentage, whole-body fat mass, whole-body fat-free mass were estimated. Hand grip strength (for each hand) was measured using the Jamar Hydraulic hand dynamometer. Left calcaneal bone mineral density (BMD) was measured using a Norland McCue Contact Ultrasound Bone Analyzer, from which a heel BMD t-score was calculated for each participant. At the second instant of follow-up (2014), a dual energy X-ray absorptiometry (DXA) scan was used to measure left femoral neck BMD (from which femoral neck BMD t-scores were calculated), and total bone mineral content (BMC).

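### SAP section 8.3 dates every mediator to recruitment, but femoral-neck BMD and bone mineral content come only from a 2014 scan, so neither permitted method can be applied to them

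*SAP*

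**What the plan says.** Section 8.3 opens its list with "Potential mediators include (all measured at recruitment". The list includes BMD at the heel and femoral neck, qualified by "depending on availability of data and number of participants with each measure", and bone mineral content, which has no such qualifier. For each mediator the authors will then choose between the recruitment measure, carried forward to represent the study period, and a second option, to "calculate changes in the mediator variable of interest from recruitment to the latest measurement during follow-up". The choice depends on data availability, and there is no third option. Mediation is to be tested by inverse odds ratio weighting (IORW), giving natural direct and indirect effects.

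Section 11.1.2 says: "At the second instant of follow-up (2014), a dual energy X-ray absorptiometry (DXA) scan was used to measure left femoral neck BMD", "and total bone mineral content (BMC"). No recruitment value of either variable is described anywhere in the SAP. Section 2.0 places participants' age range "at recruitment in 2006-2010".

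On time at risk, section 5.0 states: "The timeframe will be person-years until hip fracture incidence, or until end of study period or death in non-cases". Time runs from study entry, and section 8.1.3 makes attained age the timescale.

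**The concern.** The two sections cannot both be right about when femoral-neck BMD and bone mineral content were measured. This is more than a wording slip, because the methods in section 8.3 depend on it: with no recruitment DXA value, an analyst following the plan has no permitted way to handle these two mediators.

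Natural direct and indirect effects need the order exposure, then mediator, then outcome. The SAP does not say how a 2014 value would be used. If it were entered into a model with time at risk from recruitment, a participant could fracture a hip in, say, 2011 and contribute a mediator value measured afterwards. The estimated indirect effect could then partly reflect the effect of the fracture on later bone density. It could also reflect selection, since only people who survived to the scan and attended it have a value. Mediation is a stated secondary objective (section 1.2), and bone density is an obvious pathway from diet to hip fracture, so readers would give such a result weight.

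**Working it through.** The SAP states no figure on this point, so the check compares the sections and then works out the dates.

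**Step 1: timing of the bone and body measures**

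| Mediator | Timing claimed in 8.3 | Timing described in 11.1.2 |
|---|---|---|
| BMI, bioimpedance measures | recruitment | recruitment visit |
| Grip strength, heel BMD (ultrasound) | recruitment | described with the recruitment-visit measures |
| Femoral-neck BMD (DXA) | recruitment | 2014 follow-up visit |
| Bone mineral content (DXA) | recruitment | 2014 follow-up visit |

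**Step 2: can either option be applied to the DXA measures?**

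- Option 1 needs the recruitment value. None is described.
- Option 2 needs the latest value minus the recruitment value. The second term is again missing.

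Neither can be applied.

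**Step 3: delay from recruitment to scan.** The year 2014 is read as any day in that year.

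- Shortest: 31 Dec 2010 to 1 Jan 2014 = 3.0 years.
- Longest: 1 Jan 2006 to 31 Dec 2014 = 9.0 years.

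**Step 4: share of maximum follow-up before the scan.** Share = (scan date − recruitment date) / (censoring date − recruitment date). It rises with earlier recruitment and with a later scan, so the two pairings in step 3 give the bounds. Censoring dates are from section 5.0; the earliest is "the Patient Episode Database for Wales until 28th Feb 2018".

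| Country | Censoring date | Follow-up, late recruit / early recruit (years) | Lowest share | Highest share |
|---|---|---|---|---|
| England | 30 Sept 2021 | 10.75 / 15.75 | 3.0/10.75 = 0.28 | 9.0/15.75 = 0.57 |
| Scotland | 31 July 2021 | 10.58 / 15.58 | 3.0/10.58 = 0.28 | 9.0/15.58 = 0.58 |
| Wales | 28 Feb 2018 | 7.16 / 12.16 | 3.0/7.16 = 0.42 | 9.0/12.16 = 0.74 |

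These are shares of time, not of fractures. The SAP gives no incidence by year of follow-up, so the share of fractures before the scan cannot be derived.

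**Step 5: does another part of the SAP secure the order?**

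- Sensitivity analysis 4 in section 8.4 drops cases in the first three years. It is not tied to the mediation analysis. The shortest delay is already 3.0 years and the longest 9.0, so it would not secure the order.
- Section 9.0 deals with missing covariates, not with mediators measured after entry.
- Section 5.0 ends person-time at the fracture. If follow-up in option 2 means time at risk, measurements after a fracture are excluded. But section 11.1.2 uses the same word for a visit, and no sentence says that a measurement must come before the fracture. This ambiguity concerns change scores for the other mediators.

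**Step 6: nutrient intakes.** Section 11.1.3 takes energy and nutrient intakes from the 24-hour recalls, which section 8.4 describes as follow-up data. The same question may arise there, but the SAP gives no dates for the recalls.

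**The case against.** The strongest reply is that section 8.3 is tentative. The mediators are candidates, femoral-neck BMD is conditional on availability, and the choice of measure is left open. With no recruitment value, the natural outcome is that the two DXA measures are not analysed across the whole cohort. The bias described would then arise only in an analysis that the SAP does not plan. The analysis is also secondary and conditional: it runs only if a diet group is significantly associated with hip fracture and the mediator differs from that in regular meat-eaters.

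Much of this stands. The availability clause could remove femoral-neck BMD, the bias is conditional, and the shares of time should not be read as effect sizes. If fracture hazard rises with age, which is an assumption here, the shares of fractures would be lower. The change-score and recall points call for clarification and are not demonstrated errors.

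The reply does not remove the contradiction. The clause in the list qualifies BMD, not bone mineral content. The later clause only governs the choice between two options that both need a recruitment value. Neither corrects the timing statement, and neither tells the analyst whether to drop a 2014 value or how to use it.

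**Conclusion.** The concern holds and should be fixed. Section 8.3 misstates the timing of femoral-neck BMD and bone mineral content, and neither of its options can be carried out for them. The case is firmest for bone mineral content, which no availability clause covers. This conclusion rests on the text alone and is held with high confidence.

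The size of any resulting bias is unknown. The shares in the working (28% at the lowest, 74% at the highest) matter only if a 2014 value is analysed with time at risk from recruitment. They assume a scan on some day in 2014 and use maximum follow-up. Recruitment-visit measures such as heel BMD, BMI, grip strength and bioimpedance are unaffected unless the change score is chosen for them. The primary hazard ratios do not depend on this point.

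**What to change.** 1. Correct the timing statement in section 8.3 and give the measurement date of each mediator, including the nutrients from the 24-hour recalls.
2. State that a mediator must be measured before the fracture, for single values and change scores alike.
3. Use recruitment measures for whole-cohort mediation, for example heel BMD, BMI, grip strength and bioimpedance.
4. Either remove the two DXA variables or say how they will be used. For any mediator measured after recruitment, including a change score to a fixed visit, start time at risk at the age at measurement and exclude participants with an earlier hip fracture.
5. Report that such results apply to people who were alive, fracture-free and attended that measurement. Delayed entry repairs the order but not the selection into scanning, so compare scanned with unscanned participants by diet group.

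The cost is SAP wording plus, if the DXA measures are kept, a later entry age for those models. Attained age is already the timescale, so the model form does not change. Events before the measurement are lost for those mediators and the population narrows. The primary analysis is unchanged.

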8.4 Sensitivity analyses

1. An adjusted model with BMI removed from the adjustment set will be presented to determine the contribution of weight management to any associations.
2. We will present an adjusted model with vegans and vegetarians separated to determine if excluding vegans from the vegetarian group alters potential associations with hip fracture risk.
3. Online follow-up 24-hour dietary recall data will be compared with touchscreen FFQ data at recruitment to check for changes in diet group over time. In cases of substantial exposure change over time (e.g., > 10% of participants changing their dietary group), models will be repeated restricted to participants who maintained their original diet group.
4. Excluding cases occurring in the first three years of follow-up to check for reverse causality.
5. Excluding participants on long-term treatment for illnesses at recruitment who may be generally unhealthier and therefore at a higher risk of hip fracture.

6. We will explore patterns of missing covariate data, and will use multiple imputation through Stata's 'mi' package in the event of substantial missing covariate data.

All analyses will be performed using Stata. Two-sided p values < 0.05 will be considered statistically significant. All analyses performed and effect sizes computed will be presented in resulting manuscripts to avoid bias in selection of the reported result.

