3.0 Data cleaning

3.1 Exclusion criteria

Participants will be excluded from all analyses for any of the following reasons:

- Unable to link dietary and lifestyle data with hospital data (e.g. no NHS number provided and unable to match with records).
- Had a hip fracture (World Health Organisation, WHO International Classification of Disease (ICD-10) codes S72.0-S72.2) or osteoporosis (ICD-10 codes M80-M82) before or on the date of recruitment.

- Outlier diet or anthropometric data (energy intake < 500 or > 5000 kcal/day or BMI < 10 or > 60 kg/m²)
- Withdrew consent during the study period.
- Biological sex assigned at birth differed to self-reported sex at recruitment.
- Unable to be classified into a diet group (e.g. responded “do not know” or “prefer not to say” for questions on meat or fish intake).

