4.2 Exposure assessment

Participants will be classified into diet groups based on responses to questions in the touchscreen food frequency questionnaire (FFQ) completed at recruitment that relate to meat, fish, eggs, or dairy consumption. These included questions on frequency of intake of oily fish, non-oily fish, processed meat, poultry, beef, lamb/mutton, pork, eggs, and dairy products. Questions on meat and fish were asked in the form of “how often do you eat [specific food or beverage?]” or similar. Valid options were 1 “never”, 2 “less than once a week”, 3 “once a week”, 4 “2-4 times a week”, 5 “5-6 times a week”, or 6 “once or more daily”. We will convert responses to these individual questions into weekly-based consumption frequencies as follows: 0, 0.5, 1, 3, 5.5, 7 servings/week.

We will sum responses to questions on intake of processed meat, poultry, beef, lamb/mutton, and pork to form total meat intake (servings/week); and questions on intake of oily and non-oily fish intake to form total fish intake (servings/week). Intake of eggs and dairy products was assessed by asking

participants “Which of the following do you never eat?”, with options of “Eggs or foods containing eggs”, “Dairy products”, “I eat all of the above”, or “Prefer not to answer”.

Diet groups will be regular meat-eaters (ate meat \geq 5 times/week), occasional meat-eaters (ate meat $<$ 5 times/week), pescatarians (reported never eating meat but ate fish), vegetarians (reported never eating meat or fish but did consume eggs or dairy products), and vegans (reported never eating meat, fish, eggs, or dairy products).

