8.1.3 Accounting for confounding

Unadjusted and adjusted cox models will be applied. Both will control for age by using attained age as the timescale. The adjustment set for the adjusted model will be informed by a DAG model, which will be constructed using the online tool DAGitty, following available guidelines on their use (3). Confounders will be considered as covariates that are 1) risk factors of the outcome; 2) associated with the exposure; and 3) not on the causal pathway (4). Potential confounders are age at recruitment, sex, region, ethnicity, socio-economic status or education, marriage, physical activity, smoking, alcohol, BMI (or height and weight), number of children, menopausal status, hormone replacement therapy (HRT) in postmenopausal women, chronic disease prevalence at recruitment, and use of nutritional supplements (either generic or supplement-specific e.g. for calcium, vitamin D, and fish oil in particular, depending on availability of data). A list of likely confounders and their derivation is summarised in Supplementary Table 1.

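### Sensitivity analysis 3 selects diet maintainers from follow-up recalls but sets no start of risk other than study entry, so a post-fracture diet report can decide whether a case is kept

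*SAP*

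**What the plan says.** Diet group is assigned from the "touchscreen food frequency questionnaire (FFQ) completed at recruitment" (SAP 4.2). Item 3 of SAP 8.4 then brings in later information: "Online follow-up 24-hour dietary recall data will be compared with touchscreen FFQ data at recruitment to check for changes in diet group over time". The restriction is conditional: "In cases of substantial exposure change over time (e.g., > 10% of participants changing their dietary group" is the example given of a trigger, after which "models will be repeated restricted to participants who maintained their original diet group".

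Time at risk is defined once, in SAP 5.0, as person-years "calculated as age at time of event or censoring minus age at study entry". On the Cox models, SAP 8.1.3 adds: "Both will control for age by using attained age as the timescale". The exclusions in SAP 3.1 remove hip fractures "before or on the date of recruitment" and no later ones. Item 4 of 8.4, "Excluding cases occurring in the first three years of follow-up to check for reverse causality", is listed as a separate analysis.

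The SAP gives no recall dates and does not say which recall counts when a participant has several. It sets no start of follow-up specific to item 3 and names no estimate with which the restricted HR is to be compared.

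**The concern.** A participant can be called a maintainer only after answering a recall, some time into follow-up. If the models are simply repeated, risk still runs from study entry, and two things follow.

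- **Selection on the outcome.** Fractures between recruitment and the recall stay in the analysis as events. Each such case is kept or dropped on a diet report that post-dates the fracture, or is lost if the participant has died or does not answer. If this happens more in one diet group than another, the HR moves for reasons unrelated to the effect of diet.
- **A changed population.** Only recall completers can be maintainers. If the restricted HR is set against the full-cohort HR, any gap mixes diet stability with who answered the recall.

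Item 3 is the plan's only analysis of diet switching. Its purpose is to show whether the main result survives once switchers are removed, and neither problem lets it do that cleanly.

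**Working it through.** The SAP computes no figure on this point, so the check is first a reading of the text and then an illustration under stated assumptions.

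**Text.** Membership is known at the recall (8.4 item 3). Risk starts at study entry (5.0). Fractures between the two are not excluded (3.1). Item 4 is neither combined with item 3 nor tied to recall dates. Nothing moves entry to the recall or limits the comparison to recalls made before the event.

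**Approximation.** Let q be the share of cases that occur before the recall. Let ρ be a group's probability of being retained as a maintainer after a fracture, divided by the same probability without one. With a rare outcome (3% in SAP 6.0), the group's apparent rate is multiplied by about 1 − q(1 − ρ). The HR is therefore multiplied by

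[1 − q(1 − ρ_veg)] / [1 − q(1 − ρ_reg)].

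If ρ is equal in both groups, the factor is 1.

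**Value of q.** The SAP gives no recall timing, so it is assumed.
- Set B: 11 years of follow-up, constant hazard, recall uniform at 1–4 years. λ = −ln(0.97)/11 = 0.00277 per year, mean recall time 2.5 years, so q ≈ 2.5 × 0.00277 / 0.03 = 0.23 (simulated 0.234).
- Set A: recall uniform at 1–5 years, rate ratio stratified by one-year age bands, q about 0.13. This value depends on the hazards assumed in that simulation and is taken here as an input.

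**Results, vegetarians against regular meat-eaters, true HR 1.00**

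| Set | Vegetarian retention without → after fracture | Approximation | Simulated, risk from recruitment | Simulated, risk from recall |
|---|---|---|---|---|
| A | 0.9 → 0.8 | 1 − 0.13 × 0.111 = 0.986 | 0.982 | 0.999–1.000 |
| A | 0.9 → 0.7 | 1 − 0.13 × 0.222 = 0.971 | 0.968 | 0.999–1.000 |
| A | 0.9 → 0.6 | 1 − 0.13 × 0.333 = 0.957 | 0.955 | 0.999–1.000 |
| B | 0.8 → 0.6 | 1 − 0.234 × 0.25 = 0.942 | 0.937 | 0.998 |
| B | 0.8 → 0.4 | 1 − 0.234 × 0.50 = 0.883 | 0.888 | 1.006 |
| B | 0.8 → 0.8 (no dependence) | 1.00 | 0.997 | 0.997 |
| B | 0.8 → 0.64, regular meat-eaters 0.9 → 0.72 (same ρ) | 1.00 | 0.993 | 0.996 |

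In every row but the last, regular meat-eaters keep a retention of 0.9 whether or not they fracture.

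With a set HR of 1.3 under Set A, the full-cohort run gave 1.312. Counting from recruitment gave 1.291, 1.278 and 1.252 for the three switching levels; counting from the recall gave 1.310–1.315. The gap between 1.3 and 1.312 shows simulation error of about 1%.

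**Absolute rates.** With equal ρ = 0.8 in Set B the factor is 1 − 0.234 × 0.2 = 0.953. The simulated rates fell from 2.77 to 2.66 and 2.64 per 1000 person-years in the two groups, with the ratio near 1. With 25% of pre-recall fractures fatal and no differential switching, they fell to 2.64 and 2.63, and the ratio was 0.997.

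**Completers.** The only count that bears on recall coverage is in the title of SAP reference 10: 207,144 participants. 207,144 / 472,337 = 0.44 of the sample assumed in 6.0. That title does not say how many have a recall after recruitment, so 44% is no more than a rough indication.

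**The case against.** The other side has good points, and most of them limit the size of the problem.

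- **Entry at recruitment is inferred.** Item 3 does not say it. It follows from the single definition in 5.0, from repeating the models, and from the absence of any exception. This stands as a caveat; the text still needs a start date.
- **A reader might infer that cases are being lost because fracture changed their diet.** The SAP says nothing of the kind, nor that such change would differ by diet group. All the HR bias in the table comes from assumed extra switching among vegetarians. What the text does support is that such a case would be dropped if it arose.
- **A reader might infer that guaranteed survival to the recall biases the HR.** The condition applies to every diet group, and exposure is fixed at recruitment. In the simulation with fatal fractures and no differential switching only the absolute rates fell, and absolute risk is planned under main analyses (8.1.1), not in item 3.
- **The shifts are small against the precision available.** SAP Table 3 gives a minimum detectable HR of 1.19 for vegetarians in the full cohort. If 44% of participants have a recall, this becomes exp(ln 1.19 / √0.44) ≈ 1.30, and about 1.32 after a further 10% are removed as switchers. The point rests on a cheap repair, not on a large expected bias.
- **The full-cohort comparator is inferred too.** The SAP does not name one. Naming one removes the ambiguity.
- **Item 4 removes early cases.** It is a separate analysis, so it does not repair item 3.

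**Conclusion.** The point holds as a defect in how item 3 is specified. Membership is defined after time zero, the only stated start of risk is study entry, and pre-recall fractures remain as events, so a report made after the outcome can decide whether a case is included.

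The consequence for the HR is conditional. With no dependence of diet change or response on fracture, or equal proportional dependence in all groups, the HR stays at about 1.00 and mainly absolute rates are understated (about 4–5% in the Set B scenarios above). With the assumed extra post-fracture switching in vegetarians, a true 1.00 becomes about 0.98–0.955 (Set A) or 0.94–0.89 (Set B). Timing, switching and retention are all assumptions, and the direction would reverse if the excess lay among regular meat-eaters.

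Separately, a gap between the restricted HR and the full-cohort HR cannot be put down to diet stability alone, because only recall completers can be in the restricted set. A reader might infer that the main result is compromised. It is not: item 3 is a conditional sensitivity analysis and leaves the primary estimate untouched.

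**What to change.** In SAP 8.4 item 3:

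1. Start time at risk at the date of the last recall used to define maintenance, as delayed entry on the attained-age scale.
2. Exclude participants with a hip fracture or censoring before that date, so that every diet report used precedes the event.
3. Fit the same model from the same start date in all recall completers, and compare the maintainer HR with that estimate instead of the full-cohort HR.

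The cost is a few lines of SAP text, one additional model run, and the loss of pre-recall cases from this sensitivity analysis only: about 13–23% of cases under the two assumed recall timings. In the simulations the change brought the ratio back to between 0.99 and 1.01 in all scenarios with a true HR of 1.00. Treating diet group as time-varying is an alternative, but it answers a somewhat different question.

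### Sensitivity analysis 4 drops early cases but does not delay entry, so on the attained-age scale its HR can shift with no reverse causality present

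*SAP*

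**What the plan says.** Section 8.4, item 4 is a single line: "Excluding cases occurring in the first three years of follow-up to check for reverse causality". The next item in the list is defined by people rather than events: "Excluding participants on long-term treatment for illnesses at recruitment". Item 4 does not say how the first three years of non-cases are handled. It also does not say whether the unadjusted or the adjusted model is used, whereas items 1 and 2 name an adjusted model.

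Three other statements determine how item 4 would be run:

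- Section 5.0 counts time at risk from study entry: "calculated as age at time of event or censoring minus age at study entry".
- Section 8.1.3 sets the timescale for the unadjusted and the adjusted model: "Both will control for age by using attained age as the timescale".
- Section 8.1.3 names age at recruitment only as a candidate covariate ("Potential confounders are age at recruitment, sex, region, ethnicity") and leaves the final set open: "The adjustment set for the adjusted model will be informed by a DAG model".

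**The concern.** On a follow-up-time scale the wording would be harmless. No event can count before year three, so the first risk set is formed at year three whether or not entry is formally delayed. On the attained-age scale this no longer holds. The risk set at age 65, say, mixes people recruited years earlier, whose fractures count, with people recruited within the last three years, whose fractures have been removed by design. The second kind adds denominator without any possible numerator.

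If the diet groups have the same entry-age distribution, this dilution is equal across groups and cancels. If one group enters younger, it has fewer recent entrants at a given attained age, is diluted less, and its HR rises. A group that enters older has its HR lowered.

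Item 4 is interpreted by comparing its HR with the main HR. If reverse causality had inflated the HR of a younger-entering group, dropping early cases should bring it down. The artefact pushes the other way and could hide part of that fall. Where there is no reverse causality, it could create an apparent change.

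**Working it through.** **Inputs from the SAP.** Entry age is 40–69 ("years at recruitment in 2006-2010", section 2.0). English data run to September 2021 ("Hospital Episode Statistics for England until 30th September 2021", section 5.0), which gives about 11–15 years of follow-up. The event-free window is 3 years (section 8.4). Incidence is 3% and the group sizes are those of section 6.0.

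**Assumed, because the SAP does not give them.** These are the gap in mean entry age between diet groups (0–4 years), the shape of the entry-age distribution, the rise in hazard with age, and a single follow-up length of 12.5 years.

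**Yardstick.** The SAP states no figure for item 4. Its Table 3 is useful for scale and reproduces with HR = exp[(1.960 + 0.842) / (SD × √events)], SD = √[p(1 − p)], and events = 3% of the group plus regular meat-eaters:

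- Occasional meat-eaters: 0.03 × 452,956 = 13,589 events, SD 0.498, HR 1.049 (stated 1.05).
- Pescatarians: 0.03 × 258,267 = 7,748 events, SD 0.199, HR 1.173 (stated 1.17).
- Vegetarians: 0.03 × 256,256 = 7,688 events, SD 0.181, HR 1.193 (stated 1.19).

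**Mechanism.** Let w_g(a) be the share of group g at risk at attained age a that is within three years of entry. Under the literal rule the rate counted at age a is approximately h_g(a) × [1 − w_g(a)]. With a true HR of 1, the apparent HR at that age is [1 − w_1(a)] / [1 − w_0(a)]. This equals 1 only if the two shares are equal. Under delayed entry w is 0 in both groups, and the ratio is 1 whatever the entry ages.

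**Size.** The large-sample attained-age Cox score equation with left truncation was solved for a true HR of 1.00. For each gap there were 36 scenarios: three entry-age shapes (uniform; normal centred at 56.5 with SD 8; normal centred at 60 with SD 9, both truncated), hazard slopes of 6%, 9% and 12% per year, incidence of 1% and 3%, and compared-group shares of 4% and 45%. The compared group is the younger-entering one. Ranges are the minimum and maximum over scenarios.

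| Gap in mean entry age | Literal rule, no age at recruitment | Literal rule, linear age at recruitment | Entry delayed 3 years |
|---|---|---|---|
| 0 years | 1.000 | 1.000 | 1.000 |
| 1 year | 1.009–1.021 | at most 1.0004 | 1.000 |
| 2 years | 1.019–1.044 | at most 1.002 | 1.000 |
| 3 years | 1.029–1.069 | at most 1.004 | 1.000 |
| 4 years | 1.041–1.097 | at most 1.007 | 1.000 |

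With 9.5 years of follow-up, an assumed value for Wales (censored in February 2018), the 4-year gap gives 1.050–1.111 without the covariate and at most 1.006 with it.

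**Second calculation under different assumptions.** With censoring spread over 11–15 years and hazard slopes of 0.08–0.14 per year, the literal rule gave 1.013–1.018 at a 1-year gap and 1.043–1.060 at 3 years. With a true HR of 1.33 and slope 0.11, it gave 1.350 at 1 year and 1.398 at 3 years, against 1.330 under delayed entry. Stratifying finely by entry age removed the shift. On the follow-up-time scale the literal and delayed-entry versions gave identical HRs.

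**The case against.** The strongest reply is that the sentence is common shorthand for delayed entry and contradicts nothing else in the SAP. An item defined by an event naturally speaks of cases, so the contrast with item 5 does not show an intention to keep the early person-time. Age at recruitment stands first in the list of potential confounders, and section 11.1.1 derives it. If it enters the adjusted model, the shift is negligible. Items 1 and 2 name an adjusted model, so item 4 probably uses one too. The entry-age gaps are assumed, and with no gap there is no shift. Even the largest 12.5-year figure, 1.097, is below the detectable HRs of 1.17 and 1.19 for pescatarians and vegetarians. No later step depends on item 4.

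Most of this stands, and it is why the point is minor. It does not remove the point. The shorthand reading is possible but unstated, and an analyst who follows the text would drop the early cases and leave entry at recruitment. Inclusion of age at recruitment is left to the DAG, in a section that also says age is dealt with through the timescale, which is a reason someone might leave it out. For occasional meat-eaters, whose detectable HR is 1.05, a 3- or 4-year gap can produce a shift of that size.

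**Conclusion.** The concern holds, as a minor point. Three conditions must coincide for a material distortion: item 4 is run literally, the diet groups differ in entry age, and age at recruitment is not in the model. The SAP neither establishes nor rules out any of them. When they coincide, the HR of the younger-entering group rises by roughly 1–2% for a 1-year gap and 4–10% for a 4-year gap, with no reverse causality present. These sizes rest on the assumed gaps, hazard slopes and follow-up. The direction, and the absence of any shift under delayed entry, do not. The main analysis and the condition that triggers the mediation analyses (section 8.3) are unaffected.

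**What to change.** Replace item 4 with wording such as: *Excluding the first three years of follow-up: participants enter the risk set at age at recruitment plus three years; those with hip fracture, death or censoring before then are excluded.* State in the same line which model is used, preferably the adjusted model of the main analysis so that the two HRs can be compared directly.

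The cost is one line of text and a changed entry time in the survival set-up. No hip fracture after year three is lost, so the case count for this analysis is the same as under the present wording.
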